6.2. Per Protocol Set

The per protocol set (PPS) will consist of FAS patients who meet all of the following criteria:

- Received 100% of the planned number of infusions during the 26 week Initial Evaluation Period
- Did not take any prohibited medications or undergo any prohibited procedures (see protocol section 9.7)
- Satisfied inclusion criteria 2 and 8, and exclusion criteria 3, 7, 10, 11, 12, 13, 15, 16, 17, 18, 21, 22 and 26

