9.7. Prohibited Medications and Procedures

Patients are prohibited from receiving any of the following medications and procedures at any time after the first dose of study drug for all patients in the study (even those who discontinue ALXN1210 treatment but remain in study) until completion of the study or early termination of the patient from the study:

- Eculizumab or other complement inhibitors
- Use of any other investigational drug or device as part of a clinical trial.
- IVIg (unless for an unrelated medical need e.g. hypogammaglobinemia)
- Rituximab
- PE/PI
- New dialysis within the first 48-hour period following the first dose of ALXN1210 unless there is a compelling medical need as assessed by (1) hypervolemia unresponsive to diuretics, (2) refractory electrolyte imbalance, or (3) new-onset uremic encephalopathy. Exceptions must be approved prior to administration of dialysis on a case-by-case basis by the Sponsor.

The following concomitant medications and procedures are allowed under certain circumstances and with the following restrictions:

- Use of other immunosuppressive therapies (such as steroids, mTORi [eg, sirolimus, everolimus], CNI [eg, cyclosporine or tacrolimus]) during the study are not allowed unless: a) part of an established post-transplant antirejection regime, or b) patient has

confirmed anti-complement factor antibodies requiring immunosuppressive therapy, or c) steroids are being used for a condition other than aHUS (eg, asthma), or d) steroids initiated empirically prior to enrollment and are being tapered as standard of care.

Any patients receiving other complement inhibitors (including eculizumab) or undergoing PE/PI after the first dose of study drug will be withdrawn from the study.

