7.1.2. Protocol Deviations

Important protocol deviations will be determined per the standard operating procedure (SOP) “Identification, Handling, and Documentation of Protocol Deviations” (SOP-G-CL-0044). The number and percent of patients with specific protocol deviations will be summarized for all enrolled patients by major and minor deviations.

To ensure completeness of the list of important protocol deviations, the following will be identified programmatically from the database:

1. Patients from whom informed consent was not obtained
2. Patients who violated any inclusion/exclusion criteria
3. Patients who took prohibited medications or underwent any prohibited procedure
4. Patients who received less than 100% of the protocol specified number of doses of study drug during the Initial Evaluation Period
5. Patients found not to satisfy one or more of the following inclusion/exclusion criteria (Inclusion Criterion number 2c or Exclusion Criteria numbers 1 and 2) whom are not discontinued from the study.

A by-patient listing of inclusion/exclusion criteria, as well as protocol deviations will be presented, separately.

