9.4.6. Adverse Events

The analysis of Adverse Events is described in detail in [Section 7.3.2](#).

Treatment-emergent AEs (TEAEs) are events with start dates and start times on or after the date and time of the first study drug dose. If the start date of an AE is partially or completely missing and the end (stop) date and time of the AE does not indicate that it occurred prior to first dose, then the determination of treatment-emergent status will be based on the following:

- If the start year is after the year of the first study drug dose, then the AE is treatment-emergent; else,

- If the start year is the same as the year of the first study drug dose and
 - the start month is missing, then the AE is treatment emergent; else if
 - the start month is present and is the same or after the month of the first study drug dose, then the AE is treatment-emergent; else,
- If the start date is completely missing, then the AE is treatment-emergent.

All other AEs are considered PreTreatment Adverse Events (PTAEs).

Related AEs are defined as possible, probable or definitely related. Unrelated AEs are defined as unlikely or not related.

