9.4.8. Concomitant Medications/Therapies

The analysis of concomitant medications and therapies is described in detail in [Section 7.1.4](#).

Concomitant medications or therapies are defined as any non-study medications or therapies that were taken or given while the patient also received study medication. A medication or therapy will be considered concomitant if the start date is on or after the date of the first study drug infusion, or if the start date is before the first infusion date and the end (stop) date is after the first infusion date. If the start date of a medication/therapy is partially or completely missing and the end (stop) date of the medication/therapy does not indicate that it ended prior to first infusion, then the determination of the concomitant status will be based on the following:

- If the start year is after the year of the first study drug infusion, then the medication/therapy is concomitant; else,
- If the start year is the same as the year of the first study drug infusion and
 - the start month is missing, then the medication/therapy is concomitant; else if
 - the start month is present and is the same or after the month of the first study drug infusion, then the medication/therapy is concomitant; else,
- If the start date is completely missing, then the medication/therapy is concomitant.

All other medications/therapies are considered Prior Medications/Therapies.

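### The per-protocol exclusion for prohibited therapy has no 26-week limit, so use in the Extension Period can remove a patient from the only listed sensitivity analysis of the 26-week endpoint

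*SAP*

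**What the plan says.** SAP 6.2 builds the PPS from FAS patients who meet three criteria.

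- The first concerns dosing and carries its own window: "Received 100% of the planned number of infusions during the 26 week Initial Evaluation Period".
- The second concerns prohibited therapy and carries none: "Did not take any prohibited medications or undergo any prohibited procedures (see protocol section 9.7".
- The third lists eligibility criteria.

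The cited Protocol 9.7 applies its prohibitions "at any time after the first dose of study drug for all patients in the study" and "until completion of the study or early termination of the patient from the study". It expressly includes patients who have stopped study drug but remain in follow-up.

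SAP 7.1.2 shows the same contrast. Its item on missed doses is limited to the Initial Evaluation Period. Its item on prohibited use is not: "Patients who took prohibited medications or underwent any prohibited procedure".

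The primary endpoint is Complete TMA Response within the 26-week period. The Table 1 footnotes in the protocol place the last assessment before the Day 183 dose, which opens the Extension Period. SAP 7.2.1.5 names the PPS as the only sensitivity analysis of this endpoint, and SAP 6.4 defines no further set.

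**The concern.** A per-protocol analysis of a 26-week endpoint should select patients on how they were treated while that endpoint was being measured. Here a patient could receive every planned infusion, have no prohibited therapy for 26 weeks and have a settled response status, yet leave the PPS because of a treatment given a year or more later.

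This has three consequences.

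- The selection conditions on events after the endpoint, and those events may be related to how the disease went.
- SAP 4.3 holds the 26-week analysis only after the last patient has finished the period. Early enrollees then already have Extension data and late enrollees have almost none, so membership depends on enrollment date.
- Protocol 15.3 fixes the FAS before the 26-week snapshot, but neither document says this for the PPS. One SAP serves both planned analyses, so the 26-week PPS could have different members in the two reports.

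**Working it through.** **Anchor: the plan's own figure.** SAP 9.3 assumes 65% response in 50 patients and a half-width of about 15%. The Gaussian term is 1.96 × √(0.65 × 0.35 / 50) = 0.132. The continuity correction adds 1/(2 × 50) = 0.010. The total, 0.142, agrees with the stated figure. The plan gives no figure for the PPS, so the rest is illustration.

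**The texts side by side.**

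| Source | Dosing | Prohibited therapy |
|---|---|---|
| SAP 6.2 | 26-week period | no period; refers to Protocol 9.7 |
| SAP 7.1.2 | Initial Evaluation Period | no period |
| Protocol 9.7 | not applicable | after first dose to study completion or early termination |

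The dialysis restriction covers only "New dialysis within the first 48-hour period following the first dose of ALXN1210", so it cannot operate in the Extension Period. The other prohibitions can: complement inhibitors, other investigational products, rituximab, plasma exchange or infusion, and non-exempt immunoglobulin and immunosuppressants.

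**Share of scheduled time after the endpoint.** Under the protocol, Day 183 to Day 1863 is 1680 of 1862 days, or 90%. With the SAP's 2-year Extension, taken to Day 911, it is 728 of 910 days, or 80%.

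**Expected numbers.** Assume a constant rate h of 1% to 5% per patient-year and full follow-up. The expected count is 55 × (1 − e^(−h·t)).

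| Interval | t (years) | Patients with prohibited use |
|---|---|---|
| First 26 weeks | 182/365.25 = 0.50 | 0.3 to 1.4 |
| 2-year Extension | 728/365.25 = 1.99 | 1.1 to 5.2 |
| Extension to Day 1863 | 1680/365.25 = 4.60 | 2.5 to 11.3 |

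**At the 26-week snapshot.** The protocol synopsis gives March 2017 for the first patient treated and estimates May 2023 for the last visit. If that last visit is Day 1863 of the last enrollee, 1862 days (about 61 months) earlier is about April 2018, which implies roughly 13 months of accrual. With even accrual, the mean Extension time when the last patient reaches Day 183 is about 6.5 months, or 0.54 years. Then 55 × 0.54 ≈ 30 patient-years, and 30 × 0.01 to 30 × 0.05 gives 0.3 to 1.5 patients.

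**Effect on the estimate.** Suppose the PPS would otherwise hold 55 patients with 36 responders (65.5%; half-width with continuity correction 13.5 points). If k patients are removed for later use, the extremes are all responders or all non-responders:

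| k | All responders | All non-responders |
|---|---|---|
| 1 | 35/54 = 64.8% | 36/54 = 66.7% |
| 3 | 33/52 = 63.5% | 36/52 = 69.2% |
| 5 | 31/50 = 62.0% | 36/50 = 72.0% |

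The documents do not show which direction is more likely.

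**The case against.** The case for leaving the text alone has four parts.

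- **Consequence.** The FAS is primary, no hypothesis test is planned (SAP 7.2.1.4) and no decision rests on the PPS. SAP 7.2.2.3 also plans response without confirmation and a dialysis-modified definition. This stands and limits the importance of the point. Those analyses vary the definition of response, however, and do not examine adherence to the protocol.
- **Timing.** The 26-week endpoint is reported in the initial study report, so use late in the Extension cannot reach that result, and nothing says that its PPS analysis will be repeated at the end. This also stands. The exposure at the first report comes from early enrollees only, which is why the snapshot count above is small.
- **Purpose.** The PPS also serves response over time, eGFR and hematologic summaries, and Protocol 6.2.2 measures secondary endpoints over the whole study. An open-ended criterion has a use there. This is a good reason not to cut the criterion at Day 183 everywhere, but not a reason to leave the 26-week endpoint without a window.
- **Review before lock.** Protocol 15.1 has medical and statistical staff decide exclusions before database lock. They may well choose sensibly, but the SAP gives them no rule, and its literal wording points the other way.

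**Conclusion.** The point holds as a gap in specification that is cheap to close. As written, prohibited use after Day 183 removes a patient from the PPS analysis of an endpoint that it cannot have influenced. The effect is probably small at the first report: about 0.3 to 1.5 patients under the assumed rates and the accrual inferred from the synopsis dates. It would be larger only if membership were re-derived for the final report. The rates are assumptions, and the FAS result is untouched.

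Two stronger readings are tempting but not supported.

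- **Day 1 treatment before the first dose.** A reader might infer that plasma exchange or dialysis given on Day 1 before the infusion is also counted. SAP 9.4.8 is date-only, "A medication or therapy will be considered concomitant if the start date is on or after the date of the first study drug infusion", whereas SAP 9.4.6 defines treatment-emergent adverse events as "events with start dates and start times on or after the date and time of the first study drug dose". But SAP 6.2 takes its definition from Protocol 9.7, which starts after the first dose and bans only new dialysis in the following 48 hours. Nothing in either document builds the PPS from the concomitant flag. Under SAP 9.4.8, a course begun before Day 1 and ended on Day 1 is not concomitant in any case. What remains is a clarification: the SAP does not say how the order of events on Day 1 is judged.
- **A PPS shown to be biased.** No counts are given, so wrongful exclusion is possible under the wording but not demonstrated.

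**What to change.** Amend SAP 6.2 as follows.

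1. For the PPS analysis of the 26-week endpoint, apply the second criterion only to prohibited use after the first infusion and before the Day 183 dose, or up to the Day 183 assessment where no dose is given. Apply the same window where the prohibited-use item of SAP 7.1.2 feeds the PPS. The deviation listing itself can stay study-wide.
2. Fix PPS membership for this endpoint before the 26-week snapshot, as Protocol 15.3 does for the FAS, and keep it for any later report of the endpoint.
3. For PPS summaries that run past Day 183, state separately how later prohibited use is handled.
4. As a clarification, say that whether use came after the first dose is judged by clock time where available.

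The cost is a few SAP sentences. The main drawback is that the PPS for the 26-week endpoint may differ from the one behind the long-term summaries, so tables must label which is used. For a few patients, sites may be asked for the time of a Day 1 procedure.

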8.1. Inclusion Criteria

Patients are eligible for enrollment in the study only if they meet all of the following criteria and none of the exclusion criteria:

1. Male or female patients ≥ 12 years of age and weighing ≥ 40 kg at the time of consent.
2. Evidence of TMA, including thrombocytopenia, evidence of hemolysis, and kidney injury, based on the following laboratory findings:
 - a. Platelet count < 150,000 per microliter (μL) during the Screening Period or within 28 days prior to the start of the Screening Period, **and**
 - b. LDH $\geq 1.5 \times$ upper limit of normal (ULN) during the Screening Period or within 28 days prior to the start of the Screening Period, and hemoglobin \leq lower limit of normal (LLN) for age and gender during the Screening Period or within 28 days prior to the start of the Screening Period, **and**
 - c. Serum creatinine level \geq ULN during the Screening Period in adults (≥ 18 years of age), or $\geq 97.5^{\text{th}}$ percentile for age ([Appendix A](#)) at Screening in adolescents (12 to < 18 years of age) (patients who require dialysis for acute kidney injury are also eligible).
3. Among patients with a kidney transplant:
 - a. Known history of aHUS prior to current kidney transplant, **or**
 - b. No known history of aHUS, and persistent evidence of TMA at least 4 days after modifying the immunosuppressive regimen (eg, suspending or reducing the dose) of calcineurin inhibitor ([CNI]; eg, cyclosporine, tacrolimus) or mammalian target of rapamycin inhibitor ([mTORi]; eg, sirolimus, everolimus).
4. Among patients with onset of TMA postpartum, persistent evidence of TMA for > 3 days after the day of childbirth.
5. To reduce the risk of meningococcal infection (*Neisseria meningitidis*), all patients must be vaccinated against meningococcal infections within 3 years prior to, or at the time of,

initiating study drug. Patients who receive a meningococcal vaccine less than 2 weeks before initiating ALXN1210 treatment must receive treatment with appropriate prophylactic antibiotics until 2 weeks after vaccination. Patients who have not been vaccinated prior to initiating ALXN1210 treatment should receive prophylactic antibiotics prior to and for at least 2 weeks after meningococcal vaccination.

6. Patients < 18 years of age must have been vaccinated against *Haemophilus influenzae* type b (Hib) and *Streptococcus pneumoniae* according to national and local vaccination schedule guidelines.

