12. Identified drug exposure-related HUS.
13. Receiving PE/PI, for 28 days or longer, prior to the start of Screening for the current TMA.
14. History of malignancy within 5 years of Screening with the exception of a nonmelanoma skin cancer or carcinoma in situ of the cervix that has been treated with no evidence of recurrence.
15. Bone marrow transplant (BMT)/hematopoietic stem cell transplant (HSCT) within the last 6 months prior to the start of Screening.
16. HUS related to known genetic defects of cobalamin C metabolism.
17. Known systemic sclerosis (scleroderma), systemic lupus erythematosus (SLE), or antiphospholipid antibody positivity or syndrome.
18. Chronic dialysis (defined as dialysis on a regular basis as renal replacement therapy for ESKD).
19. Patients receiving chronic intravenous immunoglobulin (IVIg) within 8 weeks prior the start of Screening, unless for unrelated medical condition (eg, hypogammaglobinemia); or chronic rituximab therapy within 12 weeks prior to the start of Screening.

20. Patients receiving other immunosuppressive therapies such as steroids, mTORi (eg, sirolimus, everolimus), CNI (eg, cyclosporine or tacrolimus) are excluded unless:
 - a. part of an established post-transplant antirejection regimen, or
 - b. patient has confirmed anti-complement factor antibodies requiring immunosuppressive therapy, or
 - c. steroids are being used for a condition other than aHUS (eg, asthma).
21. Participation in another interventional treatment study or use of any experimental therapy within 30 days before initiation of study drug on Day 1 in this study or within 5 half-lives of that investigational product, whichever is greater.
22. Prior use of eculizumab or other complement inhibitors.
23. Hypersensitivity to any ingredient contained in the study drug, including hypersensitivity to murine proteins.
24. Any medical or psychological condition that, in the opinion of the Investigator or Sponsor, could increase the risk to the patient by participating in the study or confound the outcome of the study.
25. Known or suspected history of drug or alcohol abuse or dependence within 1 year prior to the start of Screening.
26. Use of tranexamic acid within 7 days prior to Screening is prohibited.

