7.2.1.5. Sensitivity Analyses

The primary and selected secondary efficacy endpoints will be analyzed based on the on the PPS to determine if the results are materially different from the analysis based on the FAS.

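### The per-protocol set omits Inclusion 3 and 4, the persistence tests for transplant and postpartum TMA, so the only named sensitivity analysis of the primary endpoint cannot remove their violators

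*SAP*

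**What the plan says.** SAP 6.1 admits to the FAS patients with at least one dose and one postbaseline efficacy assessment who satisfy Inclusion 2c and Exclusions 1 and 2. SAP 6.2 builds on that set: "The per protocol set (PPS) will consist of FAS patients who meet all of the following criteria". There are three conditions:

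- every planned infusion was received in the 26-week period;
- no medication or procedure prohibited by Protocol 9.7 was used;
- a fixed list of criteria was met: "Satisfied inclusion criteria 2 and 8, and exclusion criteria 3, 7, 10, 11, 12, 13, 15, 16, 17, 18, 21, 22 and 26".

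Protocol 8.1 gives two criteria that are not on this list. Inclusion 3 applies to kidney transplant patients and can be met in either of two ways: 3a, a known history of aHUS before the current transplant, or 3b, "No known history of aHUS, and persistent evidence of TMA at least 4 days after modifying the immunosuppressive regimen" (calcineurin inhibitor or mTOR inhibitor). Inclusion 4 reads: "Among patients with onset of TMA postpartum, persistent evidence of TMA for > 3 days after the day of childbirth". The SAP gives no reason for leaving them out.

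SAP 7.2.1.5 repeats the primary analysis on the "PPS to determine if the results are materially different from the analysis based on the FAS". No other analysis appears under that heading.

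**The concern.** This is a single-arm trial, so nothing in the design separates recovery on drug from recovery that would have happened anyway. Inclusion 3b and 4 are the criteria that ask whether TMA persisted after a plausible alternative trigger was modified or had passed. If a patient was enrolled without meeting them and the TMA was resolving for that other reason, the recovery could be scored as Complete TMA Response.

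A per-protocol analysis is the natural place to see whether such patients matter. As written, the PPS keeps them, so comparing the FAS with the PPS says nothing about them. The response proportion will be read beside eculizumab results (Protocol 7.2, SAP 7.2.1), which makes an informative check worth having.

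**Working it through.** **1. Which criteria are checked.** Protocol 8.1 has Inclusion 1 to 8 and Protocol 8.2 has Exclusion 1 to 26. Taking away the PPS list and the two exclusions enforced through the FAS leaves these unchecked:

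- Inclusion 1, 3, 4, 5, 6, 7
- Exclusion 4, 5, 6, 8, 9, 14, 19, 20, 23, 24, 25

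The list does contain diagnostic exclusions: 3 (Coombs), 10 (antibody-mediated rejection), 11 (other kidney disease), 12 (drug-related HUS), 16 (cobalamin C) and 17 (scleroderma, SLE, antiphospholipid). Inclusion 3b and 4 are of the same kind.

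**2. Whether another condition catches an Inclusion 3 or 4 violator.**

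- *Inclusion 2.* Protocol 8.1 lets 2a and 2b rest on results from up to 28 days before Screening. Those may predate the drug change or fall around delivery, so they do not show persistence.
- *Exclusion 12.* It covers "Identified drug exposure-related HUS". Where persistence after drug modification was never tested, a drug cause need not have been identified.
- *Protocol 9.7.* It applies only after the first dose, so it cannot test a condition that had to hold before enrolment.
- *Replacement.* Protocol 8.3.4 covers only Inclusion 2c and Exclusions 1 and 2.

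None of the four does.

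**3. Yardstick: the plan's own precision figure.** Inputs from SAP 9.3 and 7.2.1: p = 0.65, n = 50, normal approximation with continuity correction.

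Half-width = 1.96 × √(0.65 × 0.35 / 50) + 1/(2 × 50) = 0.132 + 0.010 = 0.142.

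That is 14.2 points, which fits the stated figure of approximately 15%.

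**4. How far the PPS estimate could move.** The documents give no violator count, so this is a range under assumptions. Since 0.65 × 50 = 32.5, take 33 responders in a PPS of 50 (66.0%). Drop k violators. The low end treats all of them as responders, (33 − k)/(50 − k). The high end treats none as responders, 33/(50 − k).

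| k | All dropped were responders | None were responders | Shift from 66.0% (points) |
|---|---|---|---|
| 1 | 32/49 = 65.3% | 33/49 = 67.3% | -0.7 to +1.3 |
| 2 | 31/48 = 64.6% | 33/48 = 68.8% | -1.4 to +2.8 |
| 3 | 30/47 = 63.8% | 33/47 = 70.2% | -2.2 to +4.2 |
| 5 | 28/45 = 62.2% | 33/45 = 73.3% | -3.8 to +7.3 |

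Starting from 32/50 (64.0%), k = 5 gives 27/45 = 60.0% to 32/45 = 71.1%, a shift of -4.0 to +7.1 points. In the table's scenarios the continuity-corrected half-width runs from 14.0 to 15.3 points.

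**The case against.** The composition of a PPS is largely the sponsor's choice. The SAP states no purpose for the list, which also holds non-diagnostic items such as Inclusion 8 (consent), and it was revisited in SAP version 3. The FAS is primary and no hypothesis is tested (SAP 7.2.1.4). Protocol 8 forbids eligibility waivers, so violators may be few, and SAP 7.1.2 lists them by patient. All of this stands and keeps the point modest. A listing shows who violated a criterion, but not the response proportion without those patients.

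The subgroups in SAP 7.2.1.2 help in part. The primary analysis is repeated by kidney transplant history, and the non-transplant stratum is free of Inclusion 3 patients. It is also repeated for patients meeting all laboratory TMA criteria centrally at Day 1, of whom at least 30 are planned (Protocol 7.1). But the transplant stratum does not separate violators from the rest, there is no postpartum subgroup, and laboratory TMA at Day 1 does not show that it lasted the required interval after a drug change or delivery.

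A reader might infer that violators of Exclusions 19 and 20 also simply stay in the PPS. The documents do not support that. Protocol 9.7 prohibits rituximab, IVIg (unless for an unrelated need) and non-excepted steroids, CNI and mTORi after the first dose, so anyone who continues them on study already fails the second PPS condition. What escapes is exposure that ended before the first dose, for example "chronic rituximab therapy within 12 weeks prior to the start of Screening", and the empirical steroid taper allowed by exception (d) in 9.7. Exclusion 19 also limits background therapy; it is not a rule that separates aHUS from drug-related or pregnancy-related TMA.

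**Conclusion.** The gap is real and narrow. Inclusion 3 and 4 are missing from the PPS definition, nothing else in the FAS or PPS replaces them, and the one analysis named as a sensitivity analysis cannot show whether their violators affect the result. The primary analysis, sample size and error rates are not touched.

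Two stronger readings go beyond the documents. One is that the response rate is inflated. With 5 violators and an assumed 33/50, the PPS estimate could shift by -3.8 to +7.3 points, all within the planned half-width of about 15 points, so neither size nor direction is known. The other is that all 10 to 25 planned transplant patients are exposed. Those with known aHUS history qualify under 3a, so only those relying on 3b face the persistence test. That range is a ceiling for the transplant part, and the number of postpartum patients is not given.

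The illustration rests on an assumed PPS of 50, a response near the planning value and at most 5 violators. The case for change rests on the check being uninformative about these patients, not on demonstrated bias. It is a cheap improvement.

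**What to change.** In SAP 6.2, third bullet, make the inclusion criteria 2, 3, 4 and 8 and leave the exclusion list as it is. SAP 7.1.2 item 2 already identifies every eligibility violation programmatically, so no new data are needed. If the omission is deliberate, state the reason in SAP 6.2.

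The cost is one line of text and a possibly smaller PPS. In the illustration the half-width goes from 1.96 × √(0.66 × 0.34 / 50) + 0.01 = 14.1 points at 33/50 to at most 15.3 points at 28/45.

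Exclusions 19 and 20 are secondary and not part of this request. Exclusion 20 should not be added for now: Protocol 9.7 exception (d) allows steroids started empirically before enrolment and being tapered, while Exclusion 20 has no such exception. Adding it would remove patients whose treatment 9.7 permits. The two passages must be reconciled first.
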